### 8.3 Definition of visit windows

The protocol specified visits/weeks and corresponding time windows used for visit-wise analyses are presented in terms of days relative to the first dose in the OLE.

Different assessments may have different visit schedules. A general rule for determining a time window for each scheduled visit is to split the two consecutive scheduled visits in the middle point of the two consecutive visits. For example, the time window for visit X is from the middle point between visit (X-1) and X (exclusive) to the middle point between visit X and (X+1) (inclusive). The time window for the first post-baseline visit is from the next day of the first dose. . The details will be specified in the programming specification.

In addition, the following visits will be assigned separately (for MMSE, FAQ, and safety endpoint) if last dose date is not missing.

- Last on treatment: the last post-baseline assessment on or before last dose date.
- End of treatment: the earliest assessment on or after last dose date and before last dose date + 56 days (inclusive)
- 12 week Follow-up: the closest assessment to last dose date + 84 days after last dose date + 57 days (inclusive)

The assessments after last dose date + 8 days (inclusive) will not be included in the visit-wise analyses except end of treatment visit and 12 week Follow-up visit (the analysis flag should not be “Y”). If last dose date is missing, the assessment at early discontinuation from study drug, follow-up visits and unscheduled visits on or after early discontinuation from study drug or follow-up visits will not be included in the visit-wise analyses.

For biomarker endpoints, the following allowance after last dose date will be used. The assessments out of each allowance will not be included in the visit-wise analyses.

- Plasma Ab(1-x): last dose days + 5 days (inclusive)
- vMRI: no limitation (all assessments will be included)

If last dose date is missing, the assessment at early discontinuation from study drug, follow-up visits and unscheduled visits on or after early discontinuation from study drug or follow-up visits will not be included in the visit-wise analyses for Plasma Ab(1-x).

If there are multiple assessments for one analysis visit, the following rules will be applied in order to select one assessment.

1. Pick the closest assessment to the target day
2. Pick the assessment at scheduled visit than unscheduled visit

- Pick the earliest assessment within the same visit (day)

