##### 3.1.2 Secondary Objective(s)

- To explore the long-term effects of elenbecestat on clinical status by assessment of:
  - a. The Mini-Mental State Examination (MMSE)
  - b. The Functional Assessment Questionnaire (FAQ; also known as the Functional Activities Questionnaire)
- To explore the long-term effects of elenbecestat on:
  - a. Volumetric magnetic resonance imaging (vMRI) including, but not limited to, total hippocampal volume, left and right hippocampal volume, whole brain volume, and total ventricular volume at 24 and 48 months of treatment in the Extension Phase.
  - b. Plasma amyloid at 12, 24, 36, and 48 months of treatment in the Extension Phase

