#### 5.5.2 Secondary Efficacy Analyses

The secondary efficacy endpoints in this SAP are:

- Change from OLE baseline in MMSE and FAQ scores
- Change / percent change from OLE baseline in total hippocampal volume, left and right hippocampal volume, whole brain volume, and total ventricular volume with up to 24 and 48 months as measured by vMRI

The actual value and change (percent change, if applicable) from baseline will be summarized using descriptive statistics for OLE baseline. Due to the termination of the study, the summary statistics will not be presented graphically.

Due to the termination of the study, the relationship between efficacy endpoints and biomarker endpoints will not be explored using correlation analysis.

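### If vMRI is scheduled only at months 24 and 48, the general window rule lets a scan from the day after first dose to about month 36 be reported as Month 24

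*SAP*

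**What the plan says.** Section 8.3 (Definition of visit windows) counts days from the first Extension Phase dose and sets windows by each assessment's own calendar: "Different assessments may have different visit schedules". Its general rule is to "split the two consecutive scheduled visits in the middle point of the two consecutive visits", with the lower limit excluded and the upper limit included. For the opening window, "The time window for the first post-baseline visit is from the next day of the first dose". The details are left to a programming specification.

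Three further rules in 8.3 bear on vMRI:

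- The last-on-treatment, end-of-treatment and 12-week follow-up slots have a limited scope: "the following visits will be assigned separately (for MMSE, FAQ, and safety endpoint) if last dose date is not missing". vMRI is not in that list.
- The allowance after last dose is five days for plasma amyloid. For vMRI the entry reads "vMRI: no limitation (all assessments will be included".
- When several assessments fall in one window, the first rule is "Pick the closest assessment to the target day".

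The timing of the endpoint is worded in two ways. The objective in 3.1.2 refers to "total ventricular volume at 24 and 48 months of treatment in the Extension Phase". The endpoint in 5.5.2 reads "with up to 24 and 48 months as measured by vMRI", and 5.1.2 also says *up to*. Section 5.5.2 plans descriptive statistics only and, because of the termination, no figures.

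**The concern.** A midpoint rule works well when visits are close together. With two scheduled times 24 months apart, it gives windows so wide that the label says little about when the scan was taken. Change in brain, hippocampal and ventricular volume accumulates with time, so a mean labelled Month 24 that mixes short and long intervals does not estimate change at 24 months.

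Section 5.5 shows the prior-placebo and prior-elenbecestat groups side by side. If the groups differ in how many subjects have an early or late sole scan, the columns can differ for that reason alone. Scans taken after treatment stopped can also enter rows that the objective describes as months of treatment. With no figures planned, and no actual scan time specified for the table, a reader could not see any of this.

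**Working it through.** The SAP prints no numeric vMRI window, so there is no stated figure to reproduce. The check applies the rule in 8.3 to the times the SAP names.

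**Inputs**

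- Scheduled vMRI times: months 24 and 48 (3.1.2, 5.1.2, 5.5.2). It is assumed that there are no others.
- Boundary at the midpoint; first window opens the day after first dose; no limit after last dose (8.3).
- Maximum treatment 48 months, follow-up to week 12 after last dose (3.2).
- Conversion (assumed): 1 month = 30.4375 days, first dose on Day 1.

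**Windows**

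- Month 24 = 24 × 30.4375 = 730.5 days. Month 48 = 48 × 30.4375 = 1461 days.
- Boundary = (730.5 + 1461)/2 = 1095.75 days, that is month 36.
- Month 24 row: Day 2 to about Day 1096.
- Month 48 row: everything later. In practice this ends near (1461 + 84)/30.4375 = 50.8, or about 51 months.

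**Follow-up allowed under the Month 24 label**

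| Sole scan at month | Share of nominal 24 months |
|---|---|
| 3 | 12.5% |
| 6 | 25% |
| 12 | 50% |
| 18 | 75% |
| 36 | 150% |

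The Month 48 row is much less affected: about 36 to 51 months, or 75% to 106% of nominal.

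**What one scan could carry (assumed linear loss of r% per year; change = r × months/12)**

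| r | Month 3 | Month 24 | Month 36 |
|---|---|---|---|
| 1 | 0.25% | 2.0% | 3.0% |
| 2 | 0.5% | 4.0% | 6.0% |
| 4 | 1.0% | 8.0% | 12.0% |

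**Illustration for a group mean.** Let a share f of the Month 24 row be early scans spread evenly over months 0 to 24 (mean 12), with the rest on time. Mean scan time = 24(1 − f) + 12f.

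- f = 0.5: 18 months; 18/24 = 0.75; understated by 25%.
- f = 0.75: 15 months; 15/24 = 0.625; understated by 37.5%.
- f = 1: 12 months; 12/24 = 0.50; understated by 50%.

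Sole scans between months 24 and 36 would push the mean the other way.

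**The two endpoint wordings against the window.** If the objective's *at* governs, scans far from month 24 do not belong in the row. If *up to* governs, scans before month 24 may belong, but the window should then not extend past month 24 to month 36. The window fits neither wording.

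**The case against.** Several points on the other side stand.

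- **The schedule is not shown.** Months 24 and 48 are the analysis times in the SAP; the assessment schedule is in the protocol. Any further scheduled vMRI would narrow the windows.
- **The rule is called general and details are deferred.** A reader might infer that the SAP fixes a window of Day 2 to Day 1096. It does not; that range follows from the rule and the named times. The programming specification could be tighter, but the SAP does not require it to be.
- **Pooling may be intended.** The *up to* wording and the explicit inclusion of all vMRI assessments suggest that early scans were meant to count. That weakens a charge of mislabelling, but it does not explain a window reaching month 36 or remove the conflict with 3.1.2.
- **The closest-to-target rule protects many subjects.** Someone with an on-time scan contributes that scan. The problem is confined to subjects with no on-time scan in the window.
- **Off-schedule scans are not shown to exist.** The SAP does not say that vMRI is done at early discontinuation. A reader might take the 25% to 50% figures as the bias in this trial. The documents do not support that: the early share, the even spread and linear loss are all assumed.

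A reader might also extend the point to plasma amyloid, whose first window opens by the same rule. The documents do not support that. Plasma amyloid has four scheduled times and a five-day limit after last dose, and nothing in the SAP shows that its change accumulates with time as volume loss does.

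**Conclusion.** The point holds conditionally. If months 24 and 48 are the only scheduled vMRI times and nothing outside the SAP tightens the rule, the Month 24 row accepts scans with roughly 0% to 150% of the nominal follow-up. It has no separate place for early-discontinuation scans and no exclusion of off-drug scans. That does not fit the objective of change at 24 and 48 months of treatment, and the SAP's own endpoint wordings need reconciling.

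The number of subjects affected is unknown. Termination makes early or irregular last scans plausible, but the documents do not establish them, so the size of any distortion can be illustrated and not estimated. The analysis is secondary, exploratory and descriptive, with no hypothesis test or sample size calculation resting on it. The effect is on how the atrophy tables are labelled and read. Severity: should-fix.

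**What to change.** 1. In 8.3, override the general rule for vMRI with a bounded window around each target. For example, ±91 days gives 730.5 ± 91, about Days 640–822, and 1461 ± 91, about Days 1370–1552. Follow-up in the rows would then be about 88% to 112% and 94% to 106% of nominal.
2. Report all other scans in a separate early/other row, with actual time since the OLE baseline scan.
3. Flag every scan taken after last dose, in all rows. A bounded window alone does not remove off-drug scans.
4. Reconcile *at* in 3.1.2 with *up to* in 5.1.2 and 5.5.2.
5. Optionally, add annualised percent change as a supportive summary, limited to scans beyond a stated minimum interval. It should not be the main summary for all scans: at 3 months, annualising multiplies measurement error by 12/3 = 4, and it imposes linear loss.

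The cost is SAP wording and a derived scan-time variable. Fewer subjects will appear in the nominal Month 24 and Month 48 rows, but no scan is lost, because the rest are shown with their actual time.

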#### 3.2 Overall Study Design and Plan

The Extension Phase allows eligible subjects to receive elenbecestat 50 mg for up to 48 months (4 years).

Subjects who are enrolled in the Core Study will have the option to participate in the Extension Phase provided that they complete the Core Study (which includes 18 months of double-blind treatment and 12 weeks of Follow-up Period) and satisfy the entry criteria for the Extension Phase. Subjects who discontinue from study drug during the Core Study are not eligible to participate in the Extension Phase.

Eligible subjects who choose to participate in the Extension Phase may enter the Extension Phase immediately following the completion of Visit 20 (ie, Visit 21 procedures may be completed on the same day as Visit 20). Subjects who are eligible to participate in the Extension Phase but

who do not transition to the Extension Phase on the day of Visit 20 may enter the Extension Phase any time within 4 weeks of Visit 20. The Medical Monitor must be contacted if Visit 21 is to occur more than 4 weeks after Visit 20. For all subjects, assessments performed at V20 may serve as baseline values for the Extension Phase (ie, results of assessments conducted at Visit 21) with exceptions of laboratory assessments and vital signs, which must be repeated if Visit 21 occurs more than 10 days from Visit 20.

During the Extension Phase, subjects will receive open-label elenbecestat 50 mg per day for up to 48 months. Subjects with pending International Normalized Ratio (INR) and serum pregnancy test results (females subjects of child bearing potential only) but who are otherwise qualified may begin OLE dosing at Visit 21; however, these subjects must discontinue study drug treatment immediately if either test result meet the exclusion criteria.

Safety assessments will be performed as described in [Table 14 of the protocol](#). Subjects may discontinue from study drug for any reason. Subjects who complete 48 months of the Extension Phase treatment or who discontinue the study drug must comply with the Early Discontinuation Visit (within 7 days after the last dose of study drug) and the Follow-Up Visits (weeks 4 and 12 after the last dose of study drug).

The study will end when the last visit for the last subject has completed the Extension Phase.

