#### **8.4 Definition of duration of treatment and duration of exposure**

The duration of treatment will be calculated using the following equation.

- Duration of treatment = date of last dose of study drug – date of first dose of study drug + 1

The duration of exposure will be calculated using the following equation.

- Duration of exposure = date of last dose of study drug – date of first dose of study drug + 1

If drug interruption occurs, then the drug interruption duration will be subtracted to calculate duration of exposure. For both duration, if the date of last dose of study drug is missing, the date of early discontinuation from study drug will be used instead. If the date of early discontinuation from study drug is also missing, the date of completion or discontinuation will be used instead.

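### A missing last-dose date is replaced by the early discontinuation date for exposure (SAP 8.4) but not for the end-of-treatment and 12-week follow-up visits (SAP 8.3), so collected results drop out of the tables that report them

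*SAP*

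**What the plan says.** Section 8.3 defines three extra analysis visits relative to the last dose, on this condition: "the following visits will be assigned separately (for MMSE, FAQ, and safety endpoint) if last dose date is not missing".

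- Last on treatment is the final post-baseline assessment up to the last-dose date, with no tolerance after it.
- End of treatment is the earliest assessment from the last-dose date to 56 days later.
- The 12-week follow-up is the assessment nearest to day +84, among those from day +57 onwards.

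The same section has a rule for a missing date. It begins "If last dose date is missing, the assessment at early discontinuation from study drug, follow-up visits and unscheduled visits on or after early discontinuation" and keeps these assessments out of the visit-wise analyses.

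Section 8.4 has its own rule for the same gap: "if the date of last dose of study drug is missing, the date of early discontinuation from study drug will be used instead". It adds a second step: "If the date of early discontinuation from study drug is also missing, the date of completion or discontinuation will be used instead". Both steps are written for the two durations only.

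Section 3.2 requires that subjects who complete or stop "must comply with the Early Discontinuation Visit (within 7 days after the last dose of study drug) and the Follow-Up Visits", the latter at weeks 4 and 12 after the last dose. The laboratory summaries and shift tables (5.4.4) and the ECG shift tables (5.4.6) name the end-of-treatment and 12-week follow-up visits as reported time points.

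**The concern.** The SAP treats the early discontinuation date as good enough to close a subject's exposure, but not to label the visit made at discontinuation. It gives no reason for the difference. For a subject with no last-dose date, the laboratory, ECG and MMSE results from the discontinuation and follow-up visits are collected and then left out of the columns meant to show them.

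Safety is the primary objective, and these two time points are where a reader looks for changes at stopping and for recovery afterwards. For qualitative laboratory parameters, section 5.4.4 bases percentages on subjects with both a baseline and a relevant post-baseline result. The loss would therefore show there only as a smaller denominator.

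**Working it through.** The SAP has no figure of its own to reproduce here. The check compares the two rules and then tests whether the early discontinuation (ED) date can serve as anchor.

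**1. One subject under both rules.** Illustrative days: first dose on day 1, ED date on day 200, last-dose date missing, no interruption.

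- Section 8.4: exposure = 200 − 1 + 1 = 200 days.
- Section 8.3: no end-of-treatment visit, no 12-week follow-up visit, and the ED and follow-up assessments are excluded from visit-wise analyses.
- With the ED date as anchor in 8.3, the end-of-treatment window would be days 200 to 256 (200 + 56). Follow-up would start on day 257 (200 + 57), with target day 284 (200 + 84).

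**2. Are the labels right with the ED date as anchor?** Let d be the days from the true last dose to the ED date. Section 3.2 plans d = 0 to 7. I assume that the ED date is the date of the ED visit.

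| Visit | Days from true last dose | Days from ED date | Label with true date | Label with ED date |
|---|---|---|---|---|
| ED visit | 0 to 7 | 0 | End of treatment | End of treatment |
| Week 4 | 28 | 28 − d = 21 to 28 | Not chosen (ED visit is earlier) | Not chosen |
| Week 12 | 84 | 84 − d = 77 to 84 | 12-week follow-up | 12-week follow-up |

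The labels agree. The week-12 visit keeps its label as long as 84 − d ≥ 57, that is, d ≤ 27, so there is room beyond the planned 7 days.

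**3. Where a substituted date would mislabel.**

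- *Second fallback of 8.4.* If the date of completion or discontinuation is the week-12 visit, that visit lies at +0 and becomes end of treatment. The follow-up slot stays empty. The anchor is then 84 days late.
- *Last on treatment.* An ED visit held on the substituted date would count as on treatment, although it may be 7 days after the true last dose.
- *Scheduled-visit windows.* Section 8.3 drops assessments from last dose + 8 days. An assessment 7 days after the ED date would pass, although it may be 7 + 7 = 14 days after the true last dose.
- *Plasma amyloid.* The limit is last dose + 5 days. A sample taken on the ED date would pass at +0, although it may truly be at +7.

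**4. What the exclusion does not reach.** vMRI carries no limit in 8.3. Scheduled on-treatment visits are not among the excluded assessments. AE incidence (5.4.2) is not by visit, and TEMAV incidence (5.4.4) counts post-baseline values without reference to a visit window.

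**The case against.** The best defence is that the two sections serve different purposes. A duration needs some end date, and an approximate one will do. Labelling an assessment as on or off drug needs the real date. Section 8.4 limits its substitution to the durations, and 8.3 states its own rule openly and repeats it for plasma amyloid. On this view the difference is a prespecified choice.

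Much of that stands. The sections do not contradict each other, and no rule is missing. For last on treatment, the scheduled-visit windows and plasma amyloid, the exclusion is justified. The defence does not cover end of treatment and 12-week follow-up: their windows are wide enough that the ED date gives the same labels for visits held on schedule.

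A reader might also infer three stronger things that the SAP does not support.

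- *That every by-visit result of these subjects is lost.* vMRI and the scheduled on-treatment visits stay in.
- *That abnormal safety values go undetected.* AE and TEMAV incidence are not visit-wise, so the exclusion does not reach them. What is lost is entries in by-visit tables.
- *That the affected subjects leave irregularly, so that the loss is related to outcome.* Nothing in the SAP links a missing last-dose date to the manner of leaving. Irregular leavers with a recorded date are unaffected, and subjects lost to follow-up may have no later assessment to lose.

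**Conclusion.** The point holds as an unexplained difference between 8.3 and 8.4 that costs collected data at the end-of-treatment and 12-week follow-up visits, for MMSE, FAQ and safety endpoints. The clearest effect is on the laboratory and ECG tables that name these visits.

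Its size cannot be computed, because the SAP does not say how many subjects lack a last-dose date. If k of the n subjects otherwise contributing to a column are affected and attended the visit, the column loses k/n of its results. k may be small or zero. The point is minor, worth correcting because the correction is cheap.

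The conclusion that the ED date is a safe anchor rests on two assumptions: the recorded date is that of the ED visit, and the visits are held roughly as planned in section 3.2. If the recorded date were later than the ED visit, that visit would fall before the anchor and would not become end of treatment.

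**What to change.** In section 8.3, add a rule for MMSE, FAQ and safety endpoints: if the last-dose date is missing and the early discontinuation date is recorded, use the latter as the anchor for the end-of-treatment and 12-week follow-up visits, and flag these subjects in the listing.

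The same edit should set the limits:

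- The second fallback of 8.4 is not used as an anchor.
- Last on treatment is not assigned from a substituted date.
- The existing exclusion stays for the scheduled-visit windows, for plasma amyloid, and for subjects with no early discontinuation date.

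The cost is a short addition to the SAP and a listing flag. The date is already used in 8.4, so no new data are needed. The downside is that the true last dose may be some days before the anchor. For on-schedule visits, with discontinuation planned within 7 days of the last dose, neither label changes. If the sponsor prefers to keep the exclusion, 8.3 should say why it differs from 8.4.

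### The 5-day limit for plasma Ab(1-x) in SAP 8.3 is counted only from the final OLE dose, so samples taken well into a drug interruption stay in the visit summaries

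*SAP*

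**What the plan says.** SAP section 8.3 introduces the biomarker limits with "For biomarker endpoints, the following allowance after last dose date will be used". For plasma amyloid the limit is "Plasma Ab(1-x): last dose days + 5 days (inclusive"), and the consequence is "The assessments out of each allowance will not be included in the visit-wise analyses". For volumetric MRI there is no limit: "vMRI: no limitation (all assessments will be included").

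MMSE, FAQ and safety have a separate cut-off, also tied to the final dose: "The assessments after last dose date + 8 days (inclusive) will not be included in the visit-wise analyses except end of treatment visit" and the 12-week follow-up visit. Nothing in 8.3 mentions interruptions.

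Section 8.4 does mention them: "If drug interruption occurs, then the drug interruption duration will be subtracted to calculate duration of exposure". The same section also defines a duration of treatment, from which interruptions are not subtracted.

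Section 5.6.2 makes percent change in plasma amyloid the PD endpoint, summarised descriptively against the OLE baseline. Section 5.1.2 places the measurements at 12, 24, 36 and 48 months.

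**The concern.** A 5-day allowance makes sense only if later samples no longer reflect the drug. That reasoning depends on the time since the last tablet taken before the sample. The rule instead looks at the final tablet of the whole extension. Two samples taken in the same drug state are then treated differently because of dosing that happens after both were drawn.

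Plasma amyloid is the only PD endpoint in the SAP and is planned once a year, so a sample taken during an interruption may be a subject's only value at that visit. Where a window holds several samples, 8.3 picks the one closest to the target day without regard to dosing, so an off-drug sample can displace an on-drug one. At stake is whether the visit-wise percent change describes subjects on drug or an unknown mixture of on-drug and off-drug samples.

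**Working it through.** The SAP states no figure on this point, so there is none to reproduce. The check has two parts.

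**1. The rule applied literally.** Rule in 8.3: include the sample if sample day ≤ final dose day + 5. The days below are hypothetical.

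| | Subject A | Subject B |
|---|---|---|
| Last dose before the sample | day 330 | day 330 |
| Afterwards | interruption days 331–390, then restart | permanent stop |
| Final OLE dose | day 700 | day 330 |
| Plasma sample | day 365 | day 365 |
| Time off drug at the sample | 365 − 330 = 35 days | 365 − 330 = 35 days |
| Limit under 8.3 | 700 + 5 = 705 | 330 + 5 = 335 |
| Result under 8.3 | 365 ≤ 705, included | 365 > 335, excluded |
| Limit counted from the most recent dose before the sample | 330 + 5 = 335 | 330 + 5 = 335 |
| Result with that limit | 365 > 335, excluded | 365 > 335, excluded |

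The two samples are equally far off drug and are handled differently only because A restarted.

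**2. Possible dilution of the visit mean.** Let T be the mean on-drug percent change, f the share of included samples taken more than 5 days into an interruption, and U the mean change in those samples. Then

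reported mean = (1 − f) × T + f × U.

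The SAP gives none of T, f and U. Assume T = −50%, with U = 0 (full return to baseline) or U = −25% (half-way return):

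| f | Full return | Half-way return |
|---|---|---|
| 2% | 0.98 × (−50) = −49.0% | −49.0 − 0.5 = −49.5% |
| 5% | 0.95 × (−50) = −47.5% | −47.5 − 1.25 = −48.75% |
| 10% | 0.90 × (−50) = −45.0% | −45.0 − 2.5 = −47.5% |
| 15% | 0.85 × (−50) = −42.5% | −42.5 − 3.75 = −46.25% |

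The shift towards zero is f × 50 points with full return and half of that with half-way return. If no sample falls in an interruption, it is nil.

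**The case against.** The strongest defence is that the SAP follows a convention. In 8.4 the treatment period runs from first to last dose and spans interruptions; only exposure subtracts them. Section 8.3 follows the treatment period, and keeping values from temporary interruptions while cutting off after a permanent stop is a recognised choice. This stands for MMSE, FAQ and safety. It does not settle plasma amyloid, where the sponsor set its own short limit, which has little purpose except to keep off-drug samples out.

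A reader might infer that the whole on-treatment scheme is faulty, including the visit-wise safety tables and the definition "Last on treatment: the last post-baseline assessment on or before last dose date". The document does not support that:

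- Late MMSE, FAQ and safety values after a permanent stop are not lost; they can appear in the labelled end-of-treatment and 12-week follow-up rows.
- vMRI has no cut-off, so the asymmetry cannot arise there.
- Removing interruption values from the laboratory, ECG and vital-sign tables would take safety data out of an extension whose primary objective is safety, with no labelled row to receive them. That is a debatable trade-off, not the repair of an error.

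A reader might also infer that keeping interruption values makes the drug look better tolerated. Nothing in the SAP supports a direction: such values may have recovered or may still be abnormal. The markedly abnormal laboratory counts (5.4.4) and the QTcF counts (5.4.6) are defined on any qualifying post-baseline value and do not rest on visit selection.

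Two further points limit the weight. The size rests entirely on assumptions, and the extension was terminated, with only descriptive summaries and no sample size calculation. Section 8.3 also leaves window details to a programming specification that is not shown. However, the 5-day cut-off is fixed in the SAP text without an interruption condition, so a programmer following that text would include these samples.

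**Conclusion.** The point holds for plasma Ab(1-x) only. As written, 8.3 admits samples of any time off drug if the subject later restarts, and excludes samples of the same time off drug if the subject does not. This defeats the purpose of the 5-day limit.

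The direction, towards zero, depends on plasma amyloid reverting off drug. The limit implies this, but the SAP does not state it. The size cannot be estimated from the SAP; −49.0% to −42.5% in place of −50% illustrates 2% to 15% affected samples with full return, and partial return gives less. No test or decision rule depends on it. This is a modest but real flaw in the PD summary and should be corrected before the tables are produced.

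**What to change.** In 8.3, for plasma Ab(1-x) only, count the existing 5 days from the most recent OLE dose before the sample. Apply this before the closest-to-target-day selection, so that an excluded sample cannot displace a usable one. Keep the excluded samples in the listings, marked as taken during an interruption. No new threshold is needed.

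Leave vMRI, the visit-wise rules for MMSE, FAQ and safety, and the last-on-treatment definition as they are. At most, flag values taken during an interruption in those listings.

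The cost is one sentence in the SAP and one derivation. Section 8.4 already needs the length of each interruption; the derivation also needs start and stop dates, so confirm that they are recorded. The downside is a few fewer plasma values at some visits.
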